Subjects will be randomized to complete either aerobic, high intensity interval training, or resistance exercise videos twice weekly at home during weeks 1 and 2 and once weekly during weeks 3 and 4. Subjects will be instructed to complete the exercise for the video sessions in the same location in their home on the same day at approximately the same time. The exercise videos are approximately 30 minutes long. A list of exercises to be performed is provided in Appendix E. Subjects will also ingest a self-selected meal prior to these prescribed exercise sessions. Instructions for the exercise will be provided via video links. Subjects will be instructed to check a CBG before initiating exercise to ensure safety. Subjects will be instructed to consume a snack if glucose is <120 mg/dL and delay exercise until glucose is >80 mg/dL. Also, if glucose is >250 mg/dL, subjects will be instructed to calculate if a correction dose is needed and delay exercise until glucose is <250 mg/dL. Subjects will enter information about exercise into the T1 DEXI app. Subjects will receive reminders via phone or text to complete their exercise and to monitor adherence to protocol. Participants may also receive reminders to enter activity information through the T1DEXI app. Subjects will also be instructed to check a CBG after exercise and consume a snack if needed.

Subjects will consume a high carbohydrate dinner prepared by OHSU Bionutrition once each week on the same day at approximately the same time (but not on the exercise study video days). The meals can potentially be picked up all at once and frozen until use.

Subjects will be able to contact study staff for any issues with the devices. Study staff will follow-up with subjects every 7 days. Subjects may receive text messages from study staff with study reminders/instructions or clarification of meal photos. This visit should take approximately 1.5 hours, depending on subject experience. Participants will be asked to download his/her pump weekly or biweekly during the 28 days on study. This will allow for frequent data capture in case of a battery change or loss of power to the pump which can erase insulin data.

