Triggers for reporting unanticipated problems are seizure, hospitalization, death or any other occurrence considered serious by the PI. If ongoing monitoring of the closed-loop studies reveals studies repeatedly being terminated because of unresponsive hyperglycemia or repeated serious hypoglycemia (resulting in altered mental status, loss of consciousness, or seizure) believed not amenable to revisions in control system parameter tuning, then the study will be discontinued immediately. If studies in two subjects are stopped for severe hypoglycemia or severe hyperglycemia, then the entire study will be halted. In addition, if there is any unexpected event such as death or patient hospitalization, the studies will be stopped until the root cause is evaluated.

Any adverse event (AE) and/or unanticipated problem (UP) will be reported to the investigator monitor immediately by one of the investigators. Hypo- and hyperglycemia will not be considered AEs unless subject has positive ketones or displays symptoms of hypoglycemia such as: loss of consciousness, slurred speech, hospitalization or EMS services called. One of the investigators will always be on-call during the closed-loop studies and will write up a description of the adverse event/unanticipated problem. All reportable new information (RNI) will be reported to the IRB within five calendar days after the PI learns of the event. RNI is any information that might meet the regulatory definition of an unanticipated problem involving risks to subjects or others or serious or continuing noncompliance that might impact the criteria for IRB approval. The report will be submitted to the IRB by the principal investigator or study coordinator. A summary of all UP's and adverse events, including those that do not meet the requirement for RNI, will be submitted with the continuing review.

Confidentiality Procedures:

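### Safety rules in Monitoring Procedures are worded for closed-loop studies that this protocol does not run, and the hyperglycemia adverse-event criterion rests on ketones that no listed procedure measures

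*Combined protocol and SAP*

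**What the plan says.** All the operative rules are in the protocol's Monitoring Procedures section.

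- **Discontinuation.** If monitoring of the closed-loop studies shows repeated terminations for unresponsive hyperglycemia or repeated serious hypoglycemia, "believed not amenable to revisions in control system parameter tuning, then the study will be discontinued immediately". A parenthesis describes serious hypoglycemia by its result: loss of consciousness, a seizure or altered mental status.
- **Two-subject halt.** "If studies in two subjects are stopped for severe hypoglycemia or severe hyperglycemia, then the entire study will be halted".
- **On-call cover.** "One of the investigators will always be on-call during the closed-loop studies". The same sentence gives that investigator the task of writing up the event.
- **Adverse-event definition.** "Hypo- and hyperglycemia will not be considered AEs unless subject has positive ketones or displays symptoms of hypoglycemia such as: loss of consciousness, slurred speech". The list of examples then ends with hospitalization and a call to emergency services.

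For the home period, the Study Start-up Visit section says "Subjects will be able to contact study staff for any issues with the devices" and "Study staff will follow-up with subjects every 7 days". It also provides for phone or text reminders linked to the exercise sessions.

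**The concern.** These rules decide when the study stops, who is reachable and what counts as an adverse event. Two of them name a kind of study that this protocol does not describe. A rule that depends on tuning a controller cannot be applied where the study team tunes nothing. An on-call promise limited to closed-loop sessions does not, on its words, reach participants exercising at home with their own pumps.

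The ketone criterion is a separate gap. If a laboratory finding is what turns hyperglycemia into an adverse event, someone has to obtain the finding or ask whether one was obtained. Otherwise the adverse-event summary sent to the IRB at continuing review will miss episodes managed at home.

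**Working it through.** The check is a comparison of texts. The plan states no figure to reproduce.

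**1. Does this protocol run a control system?** The opening section gives the goal as a data set for developing a glucose prediction algorithm. The Protocol Summary has participants stay on their own pumps. RISKS and BENEFITS says they manage glucose as usual. No section describes a study controller or a tuning step. In the protocol body, the phrase closed-loop studies occurs twice, both times in Monitoring Procedures; otherwise closed-loop appears only in reference titles. A participant's own pump might be a commercial automated system, since none is excluded, but the study team would not be tuning it.

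**2. Where is investigator availability stated?** Screening (Visit 1) puts an investigator on site. The Day 28 Study Completion visit offers a consult on insulin management. For the home days there are staff contact for device problems, follow-up every 7 days and exercise reminders. None of these is described as on-call investigator cover, so the on-call sentence is the only such promise.

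**3. Which other rules still work?** The two-subject halt, the stop for death or hospitalization, the unanticipated-problem triggers (which include anything the principal investigator considers serious) and the Withdrawal Criteria for unsafe hypo- or hyperglycemia. None of these depends on closed-loop wording.

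**4. Is the halt's vocabulary consistent?** The discontinuation sentence describes serious hypoglycemia. The halt in the next sentence says severe and gives no description. The halt needs 2 of 30 participants (2/30 = 6.7%), so how one event is classified can decide it.

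**5. Where could ketones be measured?** The word occurs once, in the adverse-event definition.

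| Place in the protocol | What it lists | Ketones? |
|---|---|---|
| Screening (Visit 1) laboratory tests | A1C, blood count, metabolic set | No |
| Protocol Summary and Visit 2, home checks | Capillary glucose around exercise, for symptoms and at sensor alarms | No |
| Visit 2, pre-exercise rule | "if glucose is >250 mg/dL, subjects will be instructed to calculate if a correction dose is needed and delay exercise until glucose is <250 mg/dL" | No |
| Data Collection; Recording of Data | Glucose, insulin, activity, food and exercise, forms | No |
| Appendix B | Glucose meter, sensor, watches, phone | No |

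The count of planned ketone tests is 0. The other route by which hyperglycemia could count, hospitalization or emergency services, is grammatically an example of symptoms of hypoglycemia.

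**The case against.** The strongest reply is that this is leftover template wording. The 28-day study is the only one the protocol describes, so a sensible reader would apply the on-call sentence to it. Removed contact or consent pages may also give an emergency number. Serious events are caught elsewhere: hospitalization triggers reporting and a stop, and unsafe hyperglycemia leads to withdrawal. Most of this stands, and it is why the point is minor. It does not make the tuning condition usable or supply a route to a ketone result.

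A reader might infer more than the text supports:

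- **That 7-day follow-up is the only scheduled contact.** The Visit 2 section also plans phone or text exercise and adherence reminders. They are not described as safety calls, but they are contact.
- **That weekly follow-up contradicts immediate reporting.** The sentence reads "Any adverse event (AE) and/or unanticipated problem (UP) will be reported to the investigator monitor immediately by one of the investigators". It governs the step from investigator to monitor once an event is known, not how soon a participant's event is detected.
- **That every home day and exercise session lacks cover.** A wording error does not show that cover is absent, so multiplying it by participants and days measures nothing.
- **That Appendix C supplies a conflicting definition of severe hypoglycemia.** It is a screening questionnaire on awareness and does not grade on-study events.

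**Conclusion.** The point holds as a minor safety-monitoring correction. Two sentences, one on discontinuation and one on on-call cover, are wrong as written for this study. The tuning condition cannot be evaluated, but the other rules largely back it up. The ketone criterion can still operate when a participant tests in usual care or reaches medical care, so the consequence is under-recording of ketone-positive hyperglycemia handled at home, not a missing rule.

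How many episodes would be missed cannot be sized: the documents give no event rates and none is assumed. The conclusion rests on the text supplied; a ketone instruction or an emergency contact in removed pages would narrow it. The prediction-accuracy endpoints and the cluster analyses are unaffected.

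**What to change.** Edit Monitoring Procedures as follows.

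1. In both sentences, replace the reference to closed-loop studies with the 28-day study period, and delete the tuning condition.
2. State that hospitalization or use of emergency services for hyperglycemia is an adverse event.
3. Use one term for severe or serious hypoglycemia, and apply the description already in the section (loss of consciousness, seizure or altered mental status) to the two-subject halt.
4. At the existing 7-day contacts, ask fixed questions on severe lows, any ketone results and emergency care, and record the answers on the adverse-event form.

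A home ketone check when glucose above 250 mg/dL persists after a correction dose is optional. Without it there is still no scheduled test, and item 4 captures only results obtained in usual care.

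**Cost.** Items 1 to 3 are text edits. Item 4 uses 28/7 = 4 contacts per participant, or 30 × 4 = 120 in all, the day 28 contact being possible at the completion visit. At an assumed 2 to 5 minutes each, that is 120 × 2 = 240 minutes (4 hours) to 120 × 5 = 600 minutes (10 hours) of staff time. A few more adverse events may be recorded. The sponsor must also confirm that on-call cover extends to the home period. If it already does, item 1 adds no cost; if not, arranging it is an extra cost that the documents do not allow to be priced.

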Appendix A: Physical Activity Readiness Questionnaire

Physical Activity Readiness Questionnaire (PAR-Q) and You

Regular physical activity is fun and healthy, and increasingly more people are starting to become more active every day. Being more active is very safe for most people. However, some people should check with their doctor before they start becoming much more physically active.

If you are planning to become much more physically active than you are now, start by answering the seven questions in the box below. If you are between the ages of 15 and 69, the PAR-Q will tell you if you should check with your doctor before you start. If you are over 69 years of age, and you are not used to being very active, check with your doctor.

Common sense is your best guide when you answer these questions. Please read the questions carefully and answer each one honestly:

YES	NO	
		1. Has your doctor ever said that you have a heart condition and that you should only do physical activity recommended by a doctor?
		2. Do you feel pain in your chest when you do physical activity?
		3. In the past month, have you had chest pain when you were not doing physical activity?
		4. Do you lose your balance because of dizziness or do you ever lose consciousness?
		5. Do you have a bone or joint problem that could be made worse by a change in your physical activity?
		6. Is your doctor currently prescribing drugs (for example, water pills) for your blood pressure or heart condition?
		7. Do you know of any other reason why you should not do physical activity?

If you answered:	YES to one or more questions
	
Talk to your doctor by phone or in person BEFORE you start becoming much more physically active or BEFORE you have a fitness appraisal. Tell your doctor about the PAR-Q and which questions you answered YES.
 
 You may be able to do any activity you want – as long as you start slowly and build up gradually. Or, you may need to restrict your activities to those which are safe for you. Talk with your doctor about the kinds of activities you wish to participate in and follow his/her advice. Find out which community programs are safe and helpful for you.
NO to all questions	
Delay becoming much more active:
 
 If you are not feeling well because of a temporary illness such as a cold or a fever – wait until you feel better; or If you are or may be pregnant – talk to your doctor before you start becoming more active.

If you answered NO honestly to all PAR-Q questions, you can be reasonably sure that you can:
 
 Start becoming much more physically active – begin slowly and build up gradually. This is the safest and easiest way to go. Take part in a fitness appraisal – this is an excellent way to determine your basic fitness so that you can plan the best way for you to live actively. 	
Please note: If your health changes so that you then answer YES to any of the above questions, tell your fitness or health professional. Ask whether you should change your physical activity plan.

Informed use of the PAR-Q: Reprinted from ACSM's Health/Fitness Facility Standards and Guidelines, 1997 by American College of Sports Medicine

Appendix B: Devices
FitBit

Garmin Watch

Polar Watch

[figure not shown]
Apple Watch

Dexcom G6 Continuous Glucose Monitoring System which includes Sensor and Sensor Transmitter

Smart phone with T1 DEXI app

Contour Next Blood Glucose Meter

Appendix C: Hypoglycemia Awareness questionnaire: This survey item will be used to categorize awareness or having reduced awareness of hypoglycemia.

1. Check the category that best describes you: (check one only)

- I always have symptoms when my blood sugar is low (A)
- I sometimes have symptoms when my blood sugar is low (R)
- I no longer have symptoms when my blood sugar is low (R)

2. Have you lost some of the symptoms that used to occur when your blood sugar was low?

- Yes (R)
- No (A)

3. In the past 6 months how often have you had moderate hypoglycemia episodes? (Episodes where you might feel confused, disoriented, or lethargic and were unable to treat yourself).

- Never (A)
- Once or twice (R)
- Every other month (R)
- Once a month (R)
- More than once a month (R)

4. In the past year, how often have you had severe hypoglycemia episodes? (Episodes where you were unconscious or had a seizure and needed glucagon or intravenous glucose?)

- Never (A)
- 1 time (R)
- 2 times (R)
- 3 times (R)
- 4 times (R)
- 5 times (R)
- 6 times (R)
- 7 times (R)
- 8 times (R)
- 9 times (R)
- 10 times (R)
- 11 times (R)

- 12 or more times (R)

5. How often in the last month have you had readings < 70 mg/dl with symptoms?

- Never
- 1 to 3 times
- 1 time/week
- 2 to 3 times/week
- 4 to 5 times/week
- Almost daily

6. How often in the last month have you had readings < 70 mg/dl, without symptoms? R: 5<6, A: 6<5;

- Never
- 1 to 3 times
- 1 time/week
- 2 to 3 times/week
- 4 to 5 times/week
- Almost daily

7. How low does your blood sugar need to go before you feel symptoms?

- 60-69 mg/dl (A)
- 50-59 mg/dl (A)
- 40-49 mg/dl (R)
- < 40 mg/dl (R)

8. To what extent can you tell by your symptoms that your blood sugar is low?

- Never (R)
- Rarely (R)
- Sometimes (R)
- Often (A)

Appendix D: Exercise Video Outlines

Aerobic Exercise Video Outline		
Segment	Segment Time	Activities
Warm-Up Intro (2 min)	0:00 – 2:00	0:00: Welcome! Marching Reach Up 0:30: Side to Side Kick Back Pull Back 0:45: Side to Side Kick Back Butt Kick 1:00: Side to Side Kick Back Butt Kick Reach out 1:15: Grapevine 1:30: Grapevine with Arm Circles
Active Exercise (30 min)	Each activity is performed for 30 seconds	
 1. Modified Jump rope 2. Jumping jacks 3. Side to Side Knee Raise (alternate left/right crunch) 4. Side Steps (active recovery) 5. Modified Jump rope 6. Jumping Jacks 7. Side to Side Knee Raise (alternate left/right crunch) 8. Side Steps (active recovery) 9. Arms Alternating A, T and Y with Heal Tap 10. Left Jab Bounce (left foot forward) 11. Side Steps (active recovery) 12. Arms Alternating A, T and Y with Heal Tap 13. Right Jab Bounce (right foot forward) 14. Side Steps (active recovery) 15. Right Leg Lunge Alternate Forward Back 16. Left Leg Lunge Alternate Forward Back 17. Jog in Place Hands Raised 18. Side Steps (active recovery) 19. Right Leg Lunge Alternate Forward Back 20. Left Leg Lunge Alternate Forward Back 21. Jog in Place Hands Raised 22. Side Steps (active recovery) 23. Squat to Upper Cut (right foot forward) 24. Right Jab Bounce (right foot forward) 25. Side Steps (active recovery) 26. Squat to Upper Cut (left foot forward)

		
27. Left Jab Bounce (left foot forward)
 
28. Side Steps (active recovery)
 
29. Horse Stance Overhead Reach Side Bend/ Standing Alternating Side Bend
 
30. Side Jump with Squat Alternating Left Right
 
31. Right Lateral lunge with Right Knee Drive Pull Up
 
32. Left Lateral Lunge with Left Knee Drive Pull Up
 
33. Side steps (active recovery)
 
34. Horse Stance Overhead Reach Side Bend/ Standing Alternating Side Bend
 
35. Side Jump with Squat Alternating Left Right
 
36. Right Lateral lunge with Right Knee Drive Pull Up
 
37. Left Lateral Lunge with Left Knee Drive Pull Up
 
38. Side steps (active recovery)

--	--	--

Intermittent High-Intensity Interval Exercise Video Outline

Segment	Segment Time	Activities
Warm-Up Intro (2 min)	0:00 – 2:00	
0:00: Welcome!
 
0:15: Jog with Front Japs
 
0:30: Hip Circles Feet Apart
 
0:45: Side to Side Reach Out
 
1:00: Alternating Direction Arm Circles Feet Apart
 
1:15: Side steps (active recovery)
 
1:45: Intro for exercise

Active Exercise (30 min)	Each activity is performed for 40 seconds, followed by a 70 second cool down	
 1. High Knee Sprint with Heel Tap – 40 seconds high intensity 2. Side steps (active recovery)-10 seconds 3. Side Steps with Arm Pull Back-1 minute 4. Alternating Knee Lunges (knee touching ground) then Jump Up Arms Raised then Squat-high intensity-40 seconds 5. Side steps (active recovery)-10 seconds 6. Side Steps with Arm Pull Back-1 minute

		
7. High Plank Alternating Knee Reach – 40 seconds high intensity
 
8. Side steps (active recovery)-10 seconds
 
9. Side Steps with Arm Pull Back-1 minute
 
10. Advanced Plank (Bear Crawl) Alternating Forward Backward– 40 seconds high intensity
 
11. Side steps (active recovery)-10 seconds
 
12. Side Steps with Arm Pull Back-1 minute
 
13. Diagonal Plank Alternating Reach Out Opposite Arm Leg Back to Middle-40 seconds high intensity
 
14. Side steps (active recovery)-10 seconds
 
15. Side Steps with Arm Pull Back-1 minute
 
16. Skate-Hop Alternating Sides with Arm Lunge Forward Opposite Knee Kick Back-40 seconds high intensity
 
17. Side steps (active recovery)-10 seconds
 
18. Side Steps with Arm Pull Back-1 minute
 
19. Single Leg Crouch Down then Same Knee Forward-5 Left then 5 Right-Repeat-40 sec high intensity
 
20. Side steps (active recovery)-10 seconds
 
21. Side Steps with Arm Pull Back-1 minute
 
22. Burpee (Bent Waist Rapid Jog Arm Punches Down then Plank then Jump Up)– 40 seconds high intensity
 
23. Side steps (active recovery)-10 seconds
 
24. Side Steps with Arm Pull Back-1 minute
 
25. Lay on Back-Feet Up Knees Locked-Reach Forward to Toes-40 seconds high intensity
 
26. Side steps (active recovery)-10 seconds
 
27. Side Steps with Arm Pull Back-1 minute
 
28. Upper Body Swimmer (High Plank Alterating Arm Circle Forward)-40 seconds high intensity

--	--	---

Resistance Exercise Video Outline		
Segment	Segment Time	Activities
Warm-Up Intro (2 min 20 sec)	0:00 – 2:20	0:00: Alternating Heel Kick Forward Arm Swing

		
0:15: Arms on Hips Alternating Straight Leg Extend with Bend at Waist
 
0:30: Arms on Hips Alternating Straight Leg Extend with Bend at Waist Add Arm Sweep
 
0:45: Alternating Leg Lunge Knee 90 Degrees Arm Sweep Up
 
1:10: Crunch (Arms Behind Head Alternating Knee Touch to Elbow)
 
1:30: Scarecrow (Knees Slightly Bent Torso Forward Arms Down then Up)
 
2:00: Alternating Side Lunge Arms Up/Down
 
2:20: Toe Touches with Spread Arms/Legs

Active Exercise (28 min)
	
Each activity is performed at a controlled pace in good form. Aiming for about 2 seconds to pull the weight the entire range, holding for 1 second, then controlling the return of the movement in about another 1 seconds.
	
Set 1: (approximately 8 min) Upper Body
 
Resistance band bicep curl 3 x 8
 
Resistance band side lateral shoulder raise 3 x 8
 
Resistance band bent over row 3 x 8
 
Resistance band bent over row arm forward then back 3 x 8
 
Set 2: (approximately 10 min) Lower Body
 
Resistance band squat 3 x 8
 
Resistance band deadlift 3 x 8
 
Resistance band reverse lunge 3 x 8
 
Resistance band glut crunch with hip raise 3 x 8
 
Set 3: (approximately 10 min) Total Body and Abs
 
Resistance band side lunge to diagonal lateral raise 3 x 8/side
 
Resistance band (standing) squat with arm raise 3 x 8/side
 
Resistance band (on back) alternating opposite arm and leg extend straight 3 x 8
 
Resistance band (on back) alternating opposite arm and leg extend bent 3 x 8
 
Resistance band (standing) alternating right/left crunch 3 x 8

References

- [1] P. E. Cryer, "Diverse causes of hypoglycemia-associated autonomic failure in diabetes," (in eng), *N Engl J Med*, vol. 350, no. 22, pp. 2272-9, May 27 2004.
- [2] P. E. Cryer, "Mechanisms of hypoglycemia-associated autonomic failure in diabetes," *N Engl J Med*, vol. 369, no. 4, pp. 362-72, Jul 25 2013.
- [3] U. Pedersen-Bjergaard *et al.*, "Severe hypoglycaemia in 1076 adult patients with type 1 diabetes: influence of risk markers and selection," (in eng), *Diabetes Metab Res Rev*, vol. 20, no. 6, pp. 479-86, Nov-Dec 2004.
- [4] M. R. Rickels *et al.*, "Continuous Glucose Monitoring for Hypoglycemia Avoidance and Glucose Counterregulation in Long-Standing Type 1 Diabetes," (in eng), *J Clin Endocrinol Metab*, vol. 103, no. 1, pp. 105-114, Jan 1 2018.
